8.1.1 Screening

Screening Visit assessments are listed in [Table 3-1](#).

Screening will occur within 28 days before administration of study drug. The investigator (or an appropriate authorized designee at the study site) will obtain informed consent from each subject.

To prepare for study participation, subjects will be instructed on the study restrictions ([Section 9.3](#)).

8.1.1.1 Repetition of Screening Assessment(s)

Repetition of individual screening assessment(s) that did not meet eligibility criteria is not permitted with the following exceptions:

- If there is clear evidence of a laboratory error (e.g., hemolyzed sample) or equipment malfunction, collection of a repeat sample for the appropriate laboratory test or assessment may be permitted with the approval of the medical monitor.
- Exclusionary liver function test (LFT) levels, which may be retested within 14 days of the original screening date.

If screening spirometry measurements fail to meet acceptability and repeatability criteria as specified by American Thoracic Society/European Respiratory Society guidelines,¹⁷ repeat spirometry evaluation may be performed once.

If repeat values of the individual assessment(s) are within the eligibility criteria and completed within the screening window, then the subject is eligible for the study.

8.1.1.2 Rescreening

Subjects may only be rescreened with the approval of the medical monitor. If a subject is rescreened, all screening assessments will be repeated except for CF genotyping, follicle-stimulating hormone (FSH) level (if serum FSH level was ≥ 40 mIU/mL during prior screening), sweat chloride level, and the ophthalmologic examination (if performed within the last 3 months). If a subject is rescreened, the screening window will begin once the first rescreening assessment has been initiated.

8.1.1.3 Extension of Screening Period Window

A subject may have the Screening Period window extended by 1 week for the following reasons:

- Repetition of the Screening Period assessments (Section 8.1.1.1)
- Unexpected operational or logistic delays, or to meet the eligibility criteria.

The Screening Period window may be extended by 2 weeks for the following reason:

- Additional time to conduct ophthalmologic examinations (Section 11.6.8).

8.1.2 Treatment Period

The Treatment Period will last approximately 72 weeks. The Treatment Period can be extended up to 60 days in the event of a pulmonary exacerbation. Antibiotics taken for a pulmonary infection or exacerbation must be completed at least 28 days before the Week 72 CT scan. Subjects will be randomized to 1 of 2 treatment arms: 1 active combination treatment arm and 1 placebo arm. The dosing regimen for each treatment arm is as follows:

- VX-661/ivacaftor: VX-661 100-mg /ivacaftor 150-mg FDC (light yellow) film-coated tablet for oral administration (morning dose); ivacaftor 150-mg (light blue) film-coated tablet for oral administration (evening dose)

- Placebo: 0-mg film-coated matching placebo tablets for oral administration (1 light yellow for morning dose and 1 light blue for evening dose)

The first dose of the study drug will be administered after randomization on Day 1. Study drug administration details are given in [Section 10](#).

Study visits during the Treatment Period will occur as shown in [Table 3-2](#). Subjects will be outpatients during the Treatment Period. All visits should occur within the windows specified.

8.1.3 Follow-up

The Safety Follow-up Visit assessments are listed in [Table 3-2](#). There will be an outpatient Safety Follow-up Visit approximately 28 (\pm 7) days after the last dose of study drug for subjects who complete study drug dosing and for subjects who prematurely discontinue study drug dosing.

The Safety Follow-up Visit is not required for subjects who complete the Week 72 Visit and have enrolled in the TEZ/IVA open-label extension study, VX14-661-110 (Study 110), within 28 days after the last dose of study drug.

8.1.4 Early Termination of Treatment

If the subject prematurely discontinues study drug treatment, an Early Termination of Treatment (ETT) Visit should be scheduled as soon as possible after termination of study drug treatment. Subjects who prematurely discontinue treatment will also be required to complete the Safety Follow-up Visit, approximately 28 (\pm 7) days after their last dose of study drug. The assessments performed at the ETT Visit and Safety Follow-up Visit are listed in [Table 3-2](#).

The ETT Visit should occur within 7 days after the last dose of study drug. If the ETT Visit occurs 3 weeks or later following the last dose of study drug, then the ETT Visit will replace the Safety Follow-up Visit, and a separate Safety Follow-up Visit will not be required.

During the course of study conduct, if VX-661 in combination with ivacaftor is approved by local health authorities and is available for the treatment of the population enrolled in this study, subjects may be discontinued from this study at the discretion of the sponsor ([Section 10.6](#)). If a subject is continuing onto commercially available VX-661/ivacaftor, the ETT Visit will be completed before dosing with commercially available drug begins, and the Safety Follow-up Visit will not be required.

Alternatively, if after review of a marketing application, local health authorities decline to approve, or if clinically meaningful benefit is not demonstrated for the use of VX-661/ivacaftor for the treatment of CF in populations enrolled in this study, subjects within those populations may be discontinued after communication to investigators and institutional review boards (IRBs)/independent ethics committees (IECs) of the risks/benefits related to the safety and efficacy. If subjects are discontinued from the study, an ETT Visit should occur within 7 days after the last dose of study drug and a Safety Follow-up Visit should occur within 28 (\pm 7) days after the last dose of study drug.

If the subject withdraws from the study and also withdraws consent for disclosure of future information, no further evaluations should be performed and no additional data should be collected. Vertex may retain and continue to use any data collected before such withdrawal of consent.

8.1.5 Independent Data Monitoring Committee

Safety and tolerability data will be reviewed by an IDMC to ensure the safety of the subjects in the study (Section 12.3.5.2). Procedural details of the IDMC's structure and function, frequency of meetings, and data planned for review will be included in the IDMC charter. The IDMC charter will be finalized before the first subject is screened.

8.2 Rationale for Study Design and Study Drug Regimens

8.2.1 Study Design

This is a Phase 2, randomized, placebo-controlled, double-blind, parallel-group, multicenter study in subjects aged 12 years and older with CF who are homozygous for the *F508del-CFTR* mutation with a percent predicted forced expiratory volume in 1 second ($ppFEV_1$) ≥ 70 . A randomized, double-blind study design will avoid observer bias and reduce symptoms or outcomes arising from the subjects' knowledge of treatment.

8.2.2 Study Drug Dose and Duration

VX-661 was studied at different doses alone and in combination with ivacaftor in the Phase 2 proof-of-concept Study VX11-661-101 (Study 101). The regimen of VX-661 100 mg once daily (qd) in combination with ivacaftor 150 mg every 12 hours (q12h) (VX-661 100 mg qd/ivacaftor 150 mg q12h) provided clinically meaningful and statistically significant improvement in $ppFEV_1$ compared to placebo, while VX-661 100 mg monotherapy did not (see VX-661 Investigator's Brochure). Based on the data in Study 101, VX-661 100 mg qd/ivacaftor 150 mg q12h was selected for continued development in the ongoing Phase 3 program and this study.

Placebo control is necessary to assess the effect of VX-661/ivacaftor combination treatment over time. Use of placebo is justified because there is no approved treatment available to address the underlying cause of CF for this population in Australia. All subjects will maintain their current standard of care and concomitant medication regimen throughout the study, including the use of antibiotics and hypertonic saline. Additionally, only subjects with mild to moderate pulmonary disease (baseline $ppFEV_1 \geq 70$) will be enrolled. Furthermore, subjects who have had an acute upper or lower respiratory infection, pulmonary exacerbation, or changes in therapy (including antibiotics) for pulmonary disease within 28 days before Day 1 (first dose of study drug) will be excluded. A study showed that patients who had pulmonary exacerbations that were treated with intravenous (IV) antibiotics showed good resolution of structural and functional abnormalities comparable to CF patients in clinically stable condition [REDACTED] within 1 month of completion of antibiotic therapy.¹⁸

CF is a chronic, slowly progressive disease. It is hypothesized that a notable change will be observed during the 72-week duration of this study, based on review of the natural history progression of radiographic changes demonstrated on longitudinal studies seen on CT scans. In a 2-year natural history study in 48 children with CF, with a mean age of 11 years at the

start of the study, the mean change in the Total Brody score was +2.2 points per year.¹⁹ Based on these longitudinal studies, it is estimated that the progression of disease observed in the proposed study population is a 3.3 point increase in the Total Brody Score at Week 72. There has been 1 study that has examined the impact of CFTR modulation on structural lung disease. In 10 subjects (ages 10 to 44 years) who carried the *CFTR-G551D* mutation, Sheikh et al reported a within-treatment annual improvement of 13.6 points in the Total Brody/CF-CT score after 1 year of ivacaftor treatment.²⁰

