11 ASSESSMENTS

11.1 Timing of Assessments

The timing of assessments is shown in [Table 3-1](#) and [Table 3-2](#).

[REDACTED] For the remaining assessments, the following assessments must be performed in the following order when more than 1 assessment is required at a particular time point:

[REDACTED]

2. Standard 12-lead ECG recordings
3. Vital signs and pulse oximetry

5. Safety laboratory assessments (i.e., blood draws)

LDCTs [REDACTED] should be performed on the same day. If that is not possible for logistical reasons, LDCT [REDACTED] should be performed within ± 4 days of the scheduled visit. Day 1 LDCTs [REDACTED] must be completed before dosing. The Week 72 CT scan may be delayed for up to 60 days if the subject is recovering from a pulmonary exacerbation. The antibiotic regimen for the treatment of pulmonary exacerbation or infection must be completed at least 28 days before the Week 72 CT scan. If the 28-day antibiotic-free period is not completed before the 60-day extension ends, the subject may roll over into Study 110 and complete the CT scan within the first 30 days of enrolling in Study 110. For subjects who have not completed the 28-day antibiotic-free period after the 60-day extension ends and who choose not to enroll in Study 110, the CT scan should be completed within 1 week of the end of the 60-day extension. The medical monitor should be notified about extensions for the Week 72 CT scan. No extension is permitted for any other assessment. [REDACTED]

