12.1 Sample Size and Power

The primary endpoint is the absolute change from baseline of Total Brody/CF-CT score measured by the Brody/CF-CT score system at Week 72 using LDCT. The difference between the VX-661/ivacaftor group and the placebo group in the mean change from baseline in Total Brody/CF-CT score at Week 72 will be estimated.

This is an exploratory, Phase 2 study; the sample size is not based on statistical power. With 40 subjects (20 per arm), the study is aimed to explore changes in the Total Brody score over a 72 week period and for VX-661/ivacaftor versus placebo, based on the published literature.^{19,20}

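### Does the 3.3-point progression expected at Week 72, which the cited annual rate does not reproduce, call for a change to the plan?

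*Protocol*

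**What the plan says.** The figure stands in Protocol 8.2.2, in the paragraph that explains the 72-week duration. The paragraph opens with a qualitative expectation: "It is hypothesized that a notable change will be observed during the 72-week duration of this study". It then describes one source, which followed 48 children for two years from a mean age of 11, and reports that "the mean change in the Total Brody score was +2.2 points per year". The projection for the trial comes next. It is introduced with the words "Based on these longitudinal studies, it is estimated that the progression of disease observed in the proposed study population", and the value that the protocol then assigns to this progression "is a 3.3 point increase in the Total Brody Score at Week 72". No formula or adjustment is shown. The paragraph closes with a second figure from a different setting, 10 subjects with a G551D mutation: a "within-treatment annual improvement of 13.6 points in the Total Brody/CF-CT score after 1 year of ivacaftor treatment".

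Protocol 12.1 states: "This is an exploratory, Phase 2 study; the sample size is not based on statistical power". It gives the size as 40 subjects, 20 per arm, and cites both sources for what the study sets out to explore. SAP 6.2 says the same. Neither section states an alpha level, a power, a standard deviation or a target difference, and neither mentions 3.3.

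**The concern.** The protocol gives one natural-history rate and, in the next sentence, a Week 72 figure that the rate does not produce. The stated figure is also the larger one, so the error makes the design look slightly more favorable.

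Expected progression without treatment is a natural yardstick for the placebo arm. It is also the largest benefit to be expected if the drug does no more than stop progression. If the trial had been sized on that quantity, an overstated value would mean too few subjects for the power claimed. With no power calculation in either document, 3.3 is one of the few planning numbers that a reader can check, so a failed check draws attention.

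**Working it through.** **Inputs**

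- Rate: 2.2 points per year (Protocol 8.2.2).
- Time to the primary endpoint: 72 weeks, or 504 days (Protocol 7.1 and Table 3-2).
- Stated projection: 3.3 points (Protocol 8.2.2).

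**Reproducing the stated figure.** Linear scaling is rate × years of follow-up.

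- 2.2 × 72/52 = 3.046, or 3.05.
- In days, 2.2 × 504/365.25 = 3.04.
- Working back, 3.3 / 2.2 = 1.5 years, and 1.5 × 52 = 78 weeks.
- To reach 3.3 at 72 weeks, the rate would have to be 3.3 / (72/52) = 2.38 points per year, which the protocol does not give.

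The gap is 3.3 − 3.046 = 0.254 points, and 3.3 / 3.046 = 1.083, an overstatement of 8.3%.

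**Other readings**

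| Reading | Projected increase (points) |
|---|---|
| Week 72 visit window, 71 to 73 weeks | 3.00 to 3.09 |
| Rounding of the rate, 2.15 to 2.25 per year, at 72 weeks | 2.98 to 3.12 |
| 76 weeks (planned study duration) | 2.2 × 76/52 = 3.22 |
| 72 weeks plus a 60-day delay | 2.2 × 564/365.25 = 3.40 |
| 72 weeks counted as 18 four-week months, 72/48 = 1.5 years | 3.30 |
| 18 calendar months | 3.30 |

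Protocol 11.1 allows the delay only in one circumstance: "The Week 72 CT scan may be delayed for up to 60 days if the subject is recovering from a pulmonary exacerbation". An average follow-up of 78 weeks needs an average delay of 6 weeks, or 42 days. Since 42/60 = 70%, about seven subjects in ten would need the full delay. That is not a plausible source for the figure. The readings that return 3.30 exactly are those that take 72 weeks as 18 months. That this was the cause is an inference.

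**Tracing where the figure is used**

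- *Sample size:* Protocol 12.1 and SAP 6.2 derive nothing from it.
- *Primary analysis:* Protocol 12.3.3.1 and SAP 8.3.1 fit an ANCOVA to the change at Week 72 and report each arm's estimate and the difference, with 95% confidence intervals. No external progression value enters.
- *Interim decisions:* Protocol 12.3.5.1 and SAP 9.1 plan no interim analysis, so no futility or stopping rule can depend on it.
- *Duration:* the argument in Protocol 8.2.2 is that a noticeable change should occur. An increase of 3.05 points supports that statement about as well as 3.3 does.

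**What it would mean if the figure were used.** For illustration, take 20 per arm, a two-sided 5% level and a drug that fully halts progression. The documents give no standard deviation, so the values below are assumed.

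| Assumed SD | Power at 3.05 | Power at 3.3 |
|---|---|---|
| 5 | 49% | 55% |
| 8 | 23% | 26% |
| 10 | 16% | 18% |

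The shift is 2 to 6 percentage points. The unknown standard deviation matters far more than the slip.

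**The case for a change.** The case for a correction runs as follows. The arithmetic can be checked from the protocol alone, and neither the visit window nor rounding of the rate rescues it. The text does refer to longitudinal studies in the plural and to the proposed study population, which is aged 12 and older with ppFEV1 of at least 70, whereas the cited cohort had a mean age of 11. An unstated adjustment is therefore possible. But one that landed exactly on 1.5 times the cited rate would be a coincidence, and it ought to have been described.

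The case adds that a clinical study report could repeat 3.3 as the benchmark for the placebo arm, and that Protocol 12.1 could usefully state the precision of 20 per arm. With 36 residual degrees of freedom, the 95% half-width is t(0.975, 36) × √(2/20) = 0.64 residual SD. An interval centered on full halting of progression would then exclude zero only if the SD were below 3.046/0.641 = 4.75, against 3.3/0.641 = 5.15 with the stated figure.

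The discrepancy itself stands. The consequences drawn from it do not:

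- The figure is an expected course of disease, not a treatment difference. It becomes an effect size only under the added assumption that the drug stops progression completely.
- It is not the only number in the rationale. The same paragraph gives the annual rate itself and the 13.6-point improvement.
- The SD thresholds assume that all 40 subjects are evaluable and that success means excluding zero, a criterion the study does not adopt.
- A stated half-width would record what follows from the sample size in any case. It would alter no result, and it has no bearing on the arithmetic in 8.2.2.

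**Conclusion.** The mismatch is real: the cited rate gives about 3.05 points at Week 72 and the protocol says 3.3, a difference of 0.25 points or 8.3%. This assumes linear progression at the cited rate. Whether it is an arithmetic slip or an undescribed adjustment cannot be settled from the documents, though counting 72 weeks as 18 months is the simplest explanation.

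No change to the plan follows. The number sits in a background sentence. The sample size is expressly not power-based, the SAP does not carry the figure, and the randomized placebo arm supplies the comparison that the primary analysis needs. A reader who wants a natural-history yardstick can obtain it in one line from the stated annual rate. Correcting the sentence would change no sample size, estimate, interval or conclusion.

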8.2.3 Rationale for Study Assessments

CT [REDACTED] will be used for chest imaging. Chest CT, considered the gold standard for pulmonary imaging, is widely used in the clinical care of CF patients to diagnose structural lung abnormalities and to monitor disease progression. Chest CT offers advantages over other pulmonary endpoints because it has greater sensitivity to detect early structural lung disease even while the commonly used endpoint, ppFEV₁, is within normal range and respiratory symptoms are absent.¹⁹ Additionally, CT can demonstrate the structural abnormalities that are specific to CF lung disease and can be performed similarly in all age groups. Chest CT does carry theoretical risks due to the cumulative exposure to ionizing radiation, which is particularly important in young children who would be exposed to repeated testing sessions during a clinical trial and who now have increased life expectancy. For this reason, an LDCT algorithm will be used to minimize exposure to ionizing radiation.

[REDACTED]

[REDACTED]

For LDCT [REDACTED] the Brody/CF-CT scoring system will be used. The Brody/CF-CT scoring system has been the most frequently employed scoring system to measure structural lung disease as shown on CT in CF patients, semiquantitatively scoring the degree of structural lung disease.^{24,25,26,27,28,29} This scoring system has been extensively tested and validated.³⁰ Analyses will include change from baseline in the total Brody/CF-CT score [REDACTED]

[REDACTED]

Images will be read by 2 independent, expert central readers blinded to treatment

group. This will avoid observer bias arising from the readers' knowledge of treatment.

9 STUDY POPULATION

Eligibility will be reviewed and documented by an appropriately qualified member of the investigator's team before subjects are enrolled.

9.1 Inclusion Criteria

Subjects who meet all of the following inclusion criteria will be eligible for this study:

1. Subject (or his or her legally appointed and authorized representative) will sign and date an informed consent form (ICF), and where appropriate, assent form
2. Willing and able to comply with scheduled visits, treatment plan, study restrictions, laboratory tests, contraceptive guidelines, and other study procedures
3. Subjects (males and females), will be 12 years of age or older on the date of informed consent or, where appropriate, date of assent
4. Homozygous for the *F508del-CFTR* mutation, genotype to be confirmed with testing performed at the Screening Visit. If the *CFTR* screening genotype result is not received before randomization, a previous *CFTR* genotype laboratory report may be used to establish eligibility. *Note: Subjects who have been randomized and whose screening genotype results do not confirm study eligibility must be discontinued from the study as described in Section 9.5. CFTR genotyping may be waived if the subject has a documented result from a previous Vertex study.*
5. Confirmed diagnosis of CF³¹ defined as a sweat chloride value ≥ 60 mmol/L by quantitative pilocarpine iontophoresis. A sweat chloride test must be performed at the Screening Visit if an eligible sweat chloride value is not available in the subject's medical records and the Screening Visit value is needed to establish eligibility. For subjects using sweat chloride values documented in their medical records to establish eligibility, the sweat chloride test at the Screening Visit is optional.
6. $ppFEV_1 \geq 70\%$ of predicted normal for age, sex, and height (equations of Wang et al. or Hankinson et al.)^{36,37} during screening. Spirometry measurements must meet American Thoracic Society/European Respiratory Society criteria¹⁷ for acceptability and repeatability.
7. Stable CF disease as judged by the investigator
8. Willing to remain on a stable CF medication regimen through the end of the treatment period (up to 72 weeks) and, if applicable, the ETT visit and the Safety Follow-up Visit

9.2 Exclusion Criteria

Subjects who meet any of the following exclusion criteria will **not** be eligible for this study:

1. History of any comorbidity that, in the opinion of the investigator, might confound the results of the study or pose an additional risk in administering study drug to the subject. For example:

- History of cirrhosis with portal hypertension, and/or history of risk factors for Torsade de Pointes (e.g., familial long QT syndrome, hypokalemia, heart failure, left ventricular hypertrophy, bradycardia, myocardial infarction, cardiomyopathy, history of arrhythmia [ventricular and atrial fibrillation], obesity, acute neurologic events [subarachnoid hemorrhage, intracranial hemorrhage, cerebrovascular accident, and intracranial trauma], and autonomic neuropathy)
2. Any of the following abnormal laboratory values at Screening:
 - Hemoglobin <10 g/dL
 - Abnormal liver function defined as any 2 or more of the following: $\geq 3 \times$ upper limit of normal (ULN) aspartate aminotransferase (AST), $\geq 3 \times$ ULN alanine aminotransferase (ALT), $\geq 3 \times$ ULN gamma-glutamyl transpeptidase (GGT), $\geq 3 \times$ ULN alkaline phosphatase (ALP), or $\geq 2 \times$ ULN total bilirubin
 - Abnormal liver function defined as any increase of $\geq 5 \times$ ULN in AST or ALT
 - Abnormal renal function defined as glomerular filtration rate ≤ 50 mL/min/1.73 m² (calculated by the Modification of Diet in Renal Disease Study Equation)^{32,33} for subjects ≥ 18 years of age and ≤ 45 mL/min/1.73 m² (calculated by the Counahan-Barratt equation)³⁴ for subjects aged 12 to 17 years (inclusive)
 3. For an acute upper or lower respiratory infection, pulmonary exacerbation, or changes in therapy (including antibiotics) for pulmonary disease before Day 1 (first dose of study drug), antibiotic regimen for the treatment of a pulmonary infection must have been completed at least 28 days before Day 1 (first dose of study drug).
 4. A 12-lead ECG demonstrating QTc >450 msec at Screening. If QTc exceeds 450 msec for the screening ECG, the ECG should be repeated 2 more times during the Screening Period, and the average of the 3 QTc values should be used to determine the subject's eligibility.
 5. History of solid organ or hematological transplantation
 6. History or evidence of cataract, lens opacity, Y-suture, or lamellar rings determined to be clinically significant by the ophthalmologist during the ophthalmologic examination during the Screening Period. The ophthalmologic examination does not need to be repeated if there is documentation of an examination meeting protocol criteria that was conducted within 3 months before the Screening Period. If the subject has documentation of bilateral lens removal, an ophthalmologic examination is not required and this criterion is not applicable ([Section 11.6.8](#)).
 7. History of alcohol or drug abuse, as deemed by the investigator, in the past year, including but not limited to cannabis, cocaine, and opiates.

8. Ongoing participation in an investigational drug study (including studies investigating VX-661, lumacaftor [VX-809], and/or ivacaftor) within 30 days of screening
 - A washout period of 5 terminal half-lives of the previous investigational study drug or **30** days, whichever is longer, must elapse before screening. The duration of the elapsed time may be longer if required by local regulations.
 - Ongoing participation in a noninterventional study (including observational studies and studies requiring assessment without administration of study drug) is permitted.
9. Use of restricted medications or foods within the specified window before the first dose of study drug as defined in Section 9.3.
10. Pregnant or nursing females (females of childbearing potential must have a negative pregnancy test at Screening and Day 1 [results reviewed before dosing]).
11. Sexually active subjects of reproductive potential who are not willing to follow the contraception requirements outlined in [Section 11.6.6.1](#)
12. The subject or a close relative of the subject is the investigator or a subinvestigator, research assistant, pharmacist, study coordinator, or other staff directly involved with the conduct of the study. An adult (aged 18 years or older) who is a relative of a study staff member may be randomized in the study provided that
 - the adult lives independently of and does not reside with the study staff member or
 - the adult participates in the study at a site other than the site at which the family member is employed.
13. Colonization with organisms associated with a more rapid decline in pulmonary status (e.g., *Burkholderia cenocepacia*, *Burkholderia dolosa*, and *Mycobacterium abscessus*). For subjects who have had a history of a positive culture in the past, the investigator could be guided by the following suggested criteria for a subject to be considered free of colonization:
 - The subject should have had 2 respiratory tract cultures negative for these organisms within the past 12 months, with no subsequent positive cultures.
 - These 2 respiratory tract cultures should have been separated by at least 3 months.
 - One of these 2 respiratory tract cultures should have been obtained within the past 6 months.
14. Any contraindication to undergoing LDCT [REDACTED] as per the site's institutional guidelines

